9.6.1 List of Tables

- Response rate and corresponding 95% confidence intervals using the Wilson score method by isolate, inhibitory dilution, visit and treatment group (Placebo (C2+C4+C6+C8), T1, T3+ T5, T7).
- Precursor response rate and corresponding 95% confidence intervals using Greenwood formula by indicator/mutant pair, inhibitory dilution, visit and treatment group (Placebo (C2+C4+C6+C8), T1, T3+T5, T7).

- Summary statistics for NAb titers (minimum, 25th percentile, median, 75th percentile, maximum, mean, standard deviation) among all participants, by isolate, inhibitory dilution, visit, and treatment group (Placebo (C2+C4+C6+C8), T1, T3+T5, T7).
- Summary statistics for NAb titers (minimum, 25th percentile, median, 75th percentile, maximum, mean, standard deviation) among positive responders, by isolate, inhibitory dilution, visit, and treatment group (Placebo (C2+C4+C6+C8), T1, T3+ T5, T7).
- Summary statistics for nAb precursor response (fold difference, indicator vs. mutant virus) (minimum, 25th percentile, median, 75th percentile, maximum, mean, standard deviation) among all participants, by indicator/mutant pair, inhibitory dilution, visit, and treatment group (Placebo (C2+C4+C6+C8), T1, T3+ T5, T7).
- Summary statistics for nAb precursor response (fold difference, indicator vs. mutant virus) (minimum, 25th percentile, median, 75th percentile, maximum, mean, standard deviation) among all precursor positive participants, by indicator/mutant pair, inhibitory dilution, visit, and treatment group (Placebo (C2+C4+C6+C8), T1, T3+ T5, T7).
- Response rate comparison of treatment arms (T1 vs. T3+ T5 vs. T7).
- Precursor response rate comparison of treatment arms (T1 vs. T3+ T5 vs. T7).
- Response magnitude comparison of treatment arms among all participants (T1 vs. T3+ T5 vs. T7).
- Response magnitude comparison of treatment arms among positive responders (T1 vs. T3+ T5 vs. T7).

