Mandatory assays with visit 12 samples (2 weeks post final vaccination) will measure neutralization titers in TZM-bl cells against the Env-pseudotyped vaccine strain (CH0505TF) and a vaccine strain lineage virus that exhibits a tier 1A neutralization phenotype (CH0505.w4.3). Additional assays with the above mentioned viruses and vaccine strain lineage viruses that exhibit a tier 2 neutralization (CH0505s.G458Y.N279K.2/GnT1-, CH0505TF.gly4/GnT1-, phenotype CH0505s.G458Y.N279K.N280D.6/GnT1-, and CH505TF.gly4.S365P/GnT1-) will be performed in TZM-bl cells with visit 12 samples. Two indicator viruses, CH0505s.G458Y.N279K.2/GnT1and CH0505TF.gly4/GnT1-, were developed by [name] to detect precursors from the CH235 and CH103 bNAb lineages respectively, and are paired with mutant viruses CH0505s.G458Y.N279K.N280D.6/GnT1- and CH505TF.gly4.S365P/GnT1specificity of the nAb response. If a sample was positive for an indicator virus it wastested against the paired mutant virus; otherwise, the mutant virus was not tested. The magnitude of the precursor response is the fold difference in ID50 (or ID80) response, indicator vs. mutant virus.

Evaluated bNAb Lineages Binding		
Specificity	Indicator Virus	Knock out (mutant) Virus
CH235	CH0505s.G458Y.N279K.2/GnT1	CH0505s.G458Y.N279K.N280D.6 /GnT1
CH103	CH0505TF.gly4/GnT1-	CH505TF.gly4.S365P/GnT1-

The magnitude of the nAb response will be measured by the ID50 (ID80) neutralization titer which is defined is the serum dilution that reduced relative luminescence units (RLUs) by 50% and 80% relative to the RLUs in virus control wells (cells + virus only) after subtraction of background RLU (cells only). The response to a given virus/isolate is considered positive if the neutralization titer is above a pre-specified cutoff. The prespecified positivity cutoff for ID50 and ID80 is 10. The ID50 (ID80) titers for negative responders are censored at 5 (half of the positivity cutoff).

The magnitude of the precursor response is defined as the fold difference in ID50 (ID80) titer between the indicator virus and mutant virus. When the titer for the mutant virus is below the positivity cutoff, the precursor magnitude is right-censored and computed as the ID50 (ID80) titer for the indicator virus relative to the positivity cutoff. When the titer for the indicator virus is below the positivity cutoff, the sample is excluded from the analysis.

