A positive precursor response is defined by a more than 3-fold difference in neutralizing antibody titer, indicator virus vs. mutant virus. This same threshold is applied to the fold-difference in ID50 titer and to the fold-difference in ID80 titer.

Given the right-censoring of precursor response magnitudes, we will use the Kaplan-Meier (KM) method to estimate the distribution of the precursor response magnitude and the proportion of participants with positive precursor response. A 95% confidence interval for this proportion will be calculated using the Greenwood formula. The KM-based estimated proportion is interpreted as the precursor response rate among participants with a positive response to the indicator virus. The KM-based reverse cumulative distribution describes the distribution of the magnitude of the precursor response among participants with a positive response to the indicator virus.

Groups 3 and 5 (20 mcg CH505TF and 5 mcg GLA-SE) and Groups 2, 4, 6, and 8 (placebo) were combined for analyses.

Tables show the response rates to each virus/isolate and corresponding 95% confidence intervals calculated by the Wilson score test method [1], as well as summary statistics among positive responders and both responders and non-responders. Precursor response rates estimated using the KM method and corresponding 95% confidence intervals calculated by Greenwood formula will also be presented. Comparisons of response rates between treatment arms (T1 vs. T3+ T5 vs. T7) for each virus will be summarized. Also, comparisons of ID50 and ID80 titers for each virus between treatment arms (T1 vs. T3+ T5 vs. T7) among all participants and among positive responders will also be presented.

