9.6.2 List of Figures

- Boxplots on positive responders of neutralizing antibody titers by virus, visit, and treatment arm (Placebo (C2+C4+C6+C8), T1, T3+ T5, T7).
- Boxplots on all participants of neutralizing antibody titers by virus, visit, and treatment arm (Placebo (C2+C4+C6+C8), T1, T3+ T5, T7).
- Boxplots of positive responders of neutralizing antibody titers to indicator viruses, next to positive responders of neutralizing antibody titers to mutant viruses, by indicator/mutant virus pair, visit, and treatment arm (Placebo (C2+C4+C6+C8), T1, T3+ T5, T7)
- Boxplot on positive precursor responses for fold-difference in neutralizing antibody titer to indicator vs. mutant virus, by indicator/mutant virus pair, visit, and treatment arm (Placebo (C2+C4+C6+C8), T1, T3+ T5, T7)
- Scatterplot of indicator virus neutralizing antibody titer vs. mutant virus neutralizing antibody titer, by indicator/mutant virus pair and visit, coloring points for different treatment arms (Placebo (C2+C4+C6+C8), T1, T3+ T5, T7)
- Kaplan-Meier-based reverse cumulative distribution plot show the distribution of precursor response by cell lineage and treatment arm (Placebo (C2+C4+C6+C8), T1, T3+T5, T7)

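### The NAb precursor fold tables and fold boxplot name no censoring rule, so folds recorded as lower bounds would bias these summaries downward

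*SAP*

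**What the plan says.** SAP 9.6 fixes the titer rule: "The prespecified positivity cutoff for ID50 and ID80 is 10". Samples with a negative indicator titer leave the precursor analysis: "When the titer for the indicator virus is below the positivity cutoff, the sample is excluded from the analysis". When the indicator is positive and the mutant titer is below the cutoff, "the precursor magnitude is right-censored and computed as the ID50 (ID80) titer for the indicator virus relative to the positivity cutoff". The same section draws the consequence: because of this censoring, "we will use the Kaplan-Meier (KM) method to estimate the distribution of the precursor response magnitude", and the precursor response rate is also a Kaplan-Meier estimate, with a Greenwood interval. Positivity is defined thus: "A positive precursor response is defined by a more than 3-fold difference in neutralizing antibody titer, indicator virus vs. mutant virus".

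The output lists are less careful. SAP 9.6.1 has two fold tables, one among all participants and one among precursor-positive participants, each described as "Summary statistics for nAb precursor response (fold difference, indicator vs. mutant virus) (minimum, 25th percentile, median, 75th percentile, maximum, mean, standard deviation"). SAP 9.6.2 has a boxplot of the fold among positive precursor responses. Neither list names an estimator, a censoring flag or a lower-bound label for these displays. Elsewhere the same lists do name Greenwood (precursor response rate table) and Kaplan-Meier (reverse cumulative plot).

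**The concern.** A programmer working from the shells would compute ordinary statistics on the stored folds. Some of those folds are only lower bounds. An infant whose neutralization is abolished by the knock-out mutation is recorded at indicator titer/10, however large the true fold is. Where many infants are in that position, the tables largely describe the indicator titer and say little about lineage specificity, which is what the fold is meant to measure.

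The two fold tables are the only listed tables that summarise the precursor fold numerically, and they serve secondary endpoint 2. The arms are small (SAP 2.3: T1 n = 5, T7 n = 5, T3+T5 n = 18, pooled placebo n = 10), so one or two censored infants can set an arm's median.

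Classification is a related gap. A censored fold from an indicator titer of 10 to 30 is recorded as 1 to 3. The true fold may or may not exceed 3, and the SAP does not say whether such an infant enters the precursor-positive table and boxplot.

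**Working it through.** The plan states no figure to reproduce here. The check has three parts: the recording rule, a small worked example, and a simulation under stated assumptions.

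**1. The rule.** With indicator titer I ≥ 10, mutant titer M and cutoff 10 (SAP 9.6):

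- M ≥ 10: recorded fold = I/M, a measured value.
- M < 10: recorded fold = I/10. The true fold I/M is larger, so this is a lower bound.

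At I = 100 the censored record is 10; measured folds at M = 12, 20 and 40 are 8.3, 5 and 2.5. At a given indicator titer the knocked-out infant therefore has the largest fold that can be recorded. Across infants with different titers the order can reverse: 25/<10 is recorded as 2.5, below 200/20 = 10.

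**2. Worked example (invented titers).** Indicator/mutant pairs: 100/<10, 60/<10, 25/<10, 200/20, 90/25, 80/40. Recorded folds: 10+, 6+, 2.5+, 10, 3.6, 2, where + marks censoring.

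- Plain values: mean (10 + 6 + 2.5 + 10 + 3.6 + 2)/6 = 5.68; median (3.6 + 6)/2 = 4.8; share above 3 = 4/6 = 67%.
- Kaplan-Meier: after 2, S = 5/6 = 0.833; after 3.6 (four at risk), S = 0.833 × 3/4 = 0.625; after 10 (two at risk), S = 0.625 × 1/2 = 0.3125. The median is 10 and the share above 3 is 83%.

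One of the two largest records is itself censored, so the true maximum, mean and SD are unknown.

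**3. Simulation.** The documents give no expected titers or folds, so these are assumptions: log10 indicator titer with SD 0.4, log10 true fold with SD 0.3, the two independent, and only infants with I ≥ 10 kept (400,000 drawn per scenario).

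| True median fold | Median indicator titer before selection | Censored | Tabulated median | Censored with recorded fold ≤ 3 |
|---|---|---|---|---|
| 3 | 30 / 60 / 100 | 44% / 26% / 14% | 2.1 / 2.6 / 2.8 | 32% / 14% / 6% |
| 10 | 30 / 60 / 100 | 83% / 66% / 50% | 3.2 / 5.0 / 6.5 | 43% / 20% / 9% |
| 30 | 30 / 60 / 100 | 97% / 92% / 83% | 3.4 / 6.1 / 9.5 | 43% / 20% / 9% |

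At a titer of 30, tripling the true fold from 10 to 30 moves the tabulated median only from 3.2 to 3.4.

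A second simulation, with SD 1.2 on the log2 scale for both quantities, gave censoring of 8% to 92%. The tabulated median was 2.94 against a true 3.01 at the light end and 2.42 against 12.0 at the heavy end. Kaplan-Meier recovered the true median closely in every scenario.

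**The case against.** **The governing method is already stated.** SAP 9.6 adopts Kaplan-Meier for the magnitude distribution, and 9.6.1 is a list of output titles, so the median and quartiles could be read as Kaplan-Meier quantiles. That is fair: plain treatment is inferred from silence. But the mean, SD, minimum and maximum have no stated censored-data version, and the silence stands out because neighbouring items do name their method.

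**Nothing inferential depends on these tables.** This stands. The listed precursor comparison between arms is of response rate, which is estimated by Kaplan-Meier; the magnitude comparisons described in 9.6 are of ID50 and ID80 titers. The reverse cumulative plot shows the censoring-adjusted fold distribution by arm.

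**The bias may be small, or the tables nearly empty.** With light censoring the error is slight (2.94 against 3.01). Protocol 4.1 reports that no precursors were detected by the specialized assays after the third dose in adults. The size is therefore conditional on assumed titers and folds.

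**Two stronger readings are tempting.** A reader might infer that infants with the clearest lineage-specific response receive the smallest folds. The recording rule does not support this: at a given indicator titer they receive the largest recordable fold, and in the second simulation censored infants had the higher recorded median in 7 of 12 scenarios. Their folds are understated, but they rank low only when their indicator titers are low.

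A reader might also infer that knocked-out infants vanish from the paired titer figure, described as "Boxplots of positive responders of neutralizing antibody titers to indicator viruses, next to positive responders of neutralizing antibody titers to mutant viruses". The mutant box does use positives only, which raises it. However, 9.6 draws negative responses as gray triangles and joins each participant's points, and 9.6.2 also lists all-participant boxplots and an indicator-versus-mutant scatterplot. Those infants stay visible; this is a minor display point.

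**Conclusion.** The point holds in a limited form. The SAP recognises that the fold is right-censored, then lists fold summaries and a fold boxplot with no rule for the censoring. Computed on the stored values, those summaries are biased downward. The bias is negligible with few censored folds and large with many: a true median of 10 appears as about 3.2 to 6.5, and a true median of 3 as about 2.1 to 2.8. These sizes rest on the assumed SDs, on indicator titers of 30 to 100, and on independence of titer and fold; none of these comes from the documents. That the mean, SD and maximum cannot be estimated when the largest folds are censored does not depend on those assumptions.

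The Kaplan-Meier response rate and reverse cumulative distribution are unaffected. The consequence is confined to descriptive summaries for a secondary endpoint. It is still worth correcting, because the remedy uses a method the SAP already plans.

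**What to change.** In SAP 9.6.1 and 9.6.2:

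1. In both fold tables, report the Kaplan-Meier median and quartiles, shown as ≥x or as not reached where needed, with the number and percent censored per arm.
2. Drop the plain mean, SD, minimum and maximum of the fold, or label them as computed on lower bounds.
3. Mark censored points in the fold boxplot.
4. State that a censored fold of 3 or less (indicator titer 10 to 30) is indeterminate, and is counted as neither precursor-positive nor precursor-negative outside the Kaplan-Meier estimate. At the same time align the threshold, which 9.6 gives as more than 3 in the definition and as at least 3 in the reverse cumulative plot description.
5. Optionally, in the paired titer boxplot, base the mutant box on all indicator-positive infants, with mutant-negatives at 5, the value 9.6 already assigns to negative titers.

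The cost is SAP wording and table and figure shells. No new data or methods are needed. Some quantiles will print as a bound instead of a number, which is what the data can support.

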9.6.2 List of Figures

- Boxplots on positive responders of neutralizing antibody titers by virus, visit, and treatment arm (Placebo (C2+C4+C6+C8), T1, T3+ T5, T7).
- Boxplots on all participants of neutralizing antibody titers by virus, visit, and treatment arm (Placebo (C2+C4+C6+C8), T1, T3+ T5, T7).
- Boxplots of positive responders of neutralizing antibody titers to indicator viruses, next to positive responders of neutralizing antibody titers to mutant viruses, by indicator/mutant virus pair, visit, and treatment arm (Placebo (C2+C4+C6+C8), T1, T3+ T5, T7)
- Boxplot on positive precursor responses for fold-difference in neutralizing antibody titer to indicator vs. mutant virus, by indicator/mutant virus pair, visit, and treatment arm (Placebo (C2+C4+C6+C8), T1, T3+ T5, T7)
- Scatterplot of indicator virus neutralizing antibody titer vs. mutant virus neutralizing antibody titer, by indicator/mutant virus pair and visit, coloring points for different treatment arms (Placebo (C2+C4+C6+C8), T1, T3+ T5, T7)
- Kaplan-Meier-based reverse cumulative distribution plot show the distribution of precursor response by cell lineage and treatment arm (Placebo (C2+C4+C6+C8), T1, T3+T5, T7)

9.7 Pediatric Vaccine Multiplex Assay (PVMA)

The Pediatric Vaccine Multiplex Assay (PVMA) will be used to assess EPI vaccine-specific antibody responses in infant participants, while ELISA will be used to measure recombinant hepatitis B surface antigen levels in infant participants two weeks after the fifth vaccination (Month 13, Visit 12). The following protocol objectives and endpoints will be evaluated:

Secondary objective 1:

To evaluate the effect of vaccination with CH505TF gp120 adjuvanted with GLA-SE on antibody responses to the South African Expanded Program on Immunization (EPI) schedule vaccinations *Secondary endpoint 1:*

EPI vaccine-specific antibody responses, as assessed by PVMA or ELISA 2 weeks after the 5th vaccination

The PVMA simultaneously measures antibodies against Haemophilus influenzae type B (HiB), diphtheria, tetanus, pertussis, rubella and respiratory syncytial virus (RSV). The assay developed by Itell, [name] and [name] et al. is a reliable, high-throughput technique that requires minimal sample volume and measures multiple antibody concentrations [9]. Hepatitis B-specific antibodies are measured using a 384-well ELISA format. A hepB standard is used in each assay for quality control.

The following IgG concentrations will be considered to be "protective", according to WHO recommendations: 10 mIU/mL anti-hepB IgG, 0.15 µg/mL anti-HiB IgG, 0.1 IU/mL anti-tetanus IgG, 0.1 IU/mL anti-diphtheria IgG, and 10 IU/mL anti-rubella IgG [9]. As WHO-recommended protective IgG thresholds are not available for pertussis and respiratory syncytial virus (RSV), the lower limit of quantification (LLOQ) will be used as the response threshold. For results below the LLOQ, values are truncated at LLOQ/2. For results above the upper limit of quantification (ULOQ), values are truncated at ULOQ.

The LLOQ and ULOQ of the responses are as follows:

Antigen	LLOQ	ULOQ
pertussis	0.686 IU/mL	55.6 IU/mL
RSV	0.0762 ug/mL	6.17 ug/mL

Analyses will restrict attention to participants who received all relevant recommended EPI vaccine doses prior to Month 13/Visit 12. For example, anti-HiB IgG antibodies will be evaluated in infants who received all 3 doses of DTaP-IPV-HepB-Hib. The following is the RSA EPI vaccine schedule through 12 months:

Age	Vaccines
Birth	Bacille Calmette-Guérin (BCG)
	Oral Polio Vaccine (OPV) -0
6 weeks	Oral Polio Vaccine (OPV) -1
	Rotavirus (RV) -1
	Pneumococcal conjugate (PCV) -1

	Hexavalent (DTaP-IPV-HepB-Hib) -1
10 weeks	Hexavalent (DTaP-IPV-HepB-Hib) -2
14 weeks	Rotavirus (RV) -2
	Pneumococcal conjugate (PCV) -2
	Hexavalent (DTaP-IPV-HepB-Hib) -3
6 months	Measles/Rubella (MR) -1
9 months	Pneumococcal conjugate (PCV) -3
12 months	Measles/Rubella (MR) -2

Tables will show the percent of infants with protective antibody levels or those with a detectable response and corresponding 95% confidence intervals calculated by the Wilson score test method [1], as well as summary statistics among participants with protective levels of antibodies or those with a detectable response and among all participants. Differences in the percent of infants with protective antibody levels/detectable response between vaccine and placebo groups (T1 + T3+ T5 + T7 vs. pooled placebo) will be reported alongside 95% confidence intervals for each antigen. Also, geometric mean ratios of IgG concentrations against each antigen between vaccine and placebo groups (T1 + T3+ T5 + T7 vs. pooled placebo) will be evaluated among all participants and reported alongside 95% confidence intervals.

Boxplots of concentrations of antibody will show both percent of infants with protective antibody levels/detectable responses and the distribution of IgG concentration. Participants with protective levels of antibodies/detectable responses will be indicated by dots color-coded by treatment group, and negative responses by gray triangles. Data points for each participant (if any) are connected by a grey line. Box plots based upon data from only participants with protective levels of antibodies/detectable responses are superimposed on the distributions. Alternatively, for plots including all participants, box plots based upon data from all participants are superimposed on the distributions. The mid-line of the box denotes the median and the ends of the box denote the 25th and 75th percentiles. Whiskers extend to the extreme data points that are no more than 1.5 times the interquartile range or if no value meets this criterion, to the data extremes. Scatterplots will show infant PVMA response vs. NAb response and infant PVMA response vs. BAMA IgG AUC response.

9.7.1 List of Tables

- Percent of infants with protective antibody levels or those with a detectable response and corresponding 95% confidence intervals using the Wilson score method by antigen, visit and treatment group (Placebo (C2+C4+C6+C8), T1, T3+ T5, T7).
- Summary statistics for IgG concentrations (minimum, 25th percentile, median, 75th percentile, maximum, mean, standard deviation) among all participants, by antigen, visit, and treatment group (Placebo (C2+C4+C6+C8), T1, T3+ T5, T7).

- Summary statistics for IgG concentrations (minimum, 25th percentile, median, 75th percentile, maximum, mean, standard deviation) among participants with protective levels of antibodies or those with a detectable response, by antigen, visit, and treatment group (Placebo (C2+C4+C6+C8), T1, T3+ T5, T7).
- Differences in the percent of infants with protective antibody levels/detectable response between vaccine and placebo groups (T1 + T3+ T5 + T7 vs. pooled placebo) will be reported alongside 95% confidence intervals using the Wilson score method for each antigen.
- Geometric mean ratios of IgG concentrations against each antigen between vaccine and placebo groups (T1 + T3+ T5 + T7 vs. pooled placebo) will be evaluated among all participants and reported alongside 95% confidence intervals.

9.7.2 List of Figures

- Boxplots on participants with protective levels of antibodies of IgG concentrations or those with a detectable response by antigen, visit, and treatment arm (Placebo (C2+C4+C6+C8), T1, T3+ T5, T7).
- Exploratory figures [all figures include both positive and negative responders. All figures are implemented for all vaccine groups combined, and for all placebo groups combined]
 - o Scatterplot of infant PVMA response vs. NAb response
 - o Scatterplot of infant PVMA response vs. BAMA IgG AUC response

